4.7.4 Events

Events will be described per study group on safety population, as number of events and number of infants with a certain event.

5 INTERIM ANALYSES

No interims analyses are planned.

6 CHANGES OF ANALYSIS FROM PROTOCOL

There are no significant changes from the original protocol which was submitted together with the application for ethical approval, except that the statistical analysis plan has been elaborated in more detail. However this has not resulted in any change of the protocol which could have ethical consequences.

7 LISTING OF TABLES AND FIGURES

Table	Table Title
Number	
1.1.1	Patient Disposition and Data Sets Analysed (FAS Enrolled Population)
1.1.2	Patient Disposition and Data Sets Analysed (FAS At Birth Population)
1.1.3	Patient Disposition and Data Sets Analysed (PP Enrolled Population)
1.1.4	Patient Disposition and Data Sets Analysed (PP At Birth Population)
1.2	Protocol Deviations Leading to Exclusion from PP Population (FAS Enrolled
	Population)
1.3.1	Fetal and Pregnancy Variables (FAS Enrolled Population)
1.3.2	Fetal and Pregnancy Variables (FAS At Birth Population)
1.3.3	Fetal and Pregnancy Variables (PP Enrolled Population)
1.3.4	Fetal and Pregnancy Variables (PP At Birth Population)
1.4.1	Neonatal Variables (FAS Enrolled Population)
1.4.2	Neonatal Variables (FAS At Birth Population)
1.4.3	Neonatal Variables (PP Enrolled Population)
1.4.4	Neonatal Variables (PP At Birth Population)
1.5.1	Follow-up at 2 Years Variables (FAS Enrolled Population)
1.5.2	Follow-up at 2 Years Variables (FAS At Birth Population)
1.5.3	Follow-up at 2 Years Variables (PP Enrolled Population)
1.5.4	Follow-up at 2 Years Variables (PP At Birth Population)
1.6.1	Fetal Medical and Surgical History (FAS Enrolled Population)
1.6.2	Neonatal Medical and Surgical History (FAS Enrolled Population)
1.7.1	Prior Medications (FAS Enrolled Population)
1.7.2	Concomitant Medications (FAS Enrolled Population)
2.1.1	Adjusted Analysis of Primary Efficacy Variable (FAS Enrolled Population)
2.1.2	Adjusted Analysis of Primary Efficacy Variable (FAS At Birth Population)
2.1.3	Adjusted Analysis of Primary Efficacy Variable (PP Enrolled Population)

7.1 Listing of Tables

Statistical Analysis Plan

Protocol: Effect of fetal aortic valvuloplasty on outcomes

Protocol No:

2.1.4	Adjusted Analysis of Primary Efficacy Variable (PP At Birth Population)
2.2.1	Sensitivity Analysis of Primary Efficacy Variable (FAS Enrolled Population)
2.2.2	Sensitivity Analysis of Primary Efficacy Variable (FAS At Birth Population)
2.2.3	Sensitivity Analysis of Primary Efficacy Variable (PP Enrolled Population)
2.2.4	Sensitivity Analysis of Primary Efficacy Variable (PP At Birth Population)
2.3.1	Adjusted Analysis of Secondary Efficacy Variables (FAS Enrolled Population)
2.3.2	Adjusted Analysis of Secondary Efficacy Variables (FAS At Birth Population)
2.3.3	Adjusted Analysis of Secondary Efficacy Variables (PP Enrolled Population)
2.3.4	Adjusted Analysis of Secondary Efficacy Variables (PP At Birth Population)
2.4.1.1	Descriptive Data on Primary and Secondary Variables (FAS Enrolled Population – Subgroup 1)
2.4.1.2	Descriptive Data on Primary and Secondary Variables (FAS Enrolled Population – Subgroup 2)
2.4.1.3	Descriptive Data on Primary and Secondary Variables (FAS Enrolled Population – Subgroup 3)
2.4.2.1	Descriptive Data on Primary and Secondary Variables (FAS At Birth Population – Subgroup 1)
2.4.2.2	Descriptive Data on Primary and Secondary Variables (FAS At Birth Population – Subgroup 2)
2.4.2.3	Descriptive Data on Primary and Secondary Variables (FAS At Birth Population – Subgroup 3)
3.1	Intervention and Technical Details (Safety Population)
3.2.1	Infants' Complications and Reasons for Death (Safety Population)
3.2.2	Maternal Complications (Safety Population)
3.2.3	Infants Diagnoses at Discharge (Safety Population)
3.2.4	Infants Cardiac Surgical Interventions during the Study (Safety Population)
3.3.x	Mixed Models for Repeated Data Performed on ECHO Variables (Safety Population)

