#### **Z**-scores

Z-scores for fetal cardiac measurements will be derived by gestational age (13, 14). Gestational age is automatically calculated by the eCRF system using the equation Gestational Age = (280 - (EDD - Reference Date)) / 7.

Z-scores for postnatal cardiac measurements will be derived by body surface area (15, 16).

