## Electronic case report forms (eCRF)

There are 14 eCRF's:

1. eCRF Inclusion criteria

All inclusion and no exclusion criteria need to be satisfied for a case to be included.

2. eCRF Inclusion

Include case if inclusin/exclusion criteria satisfied.

3. eCRF Counselling on fetal aortic valvuloplasty

If councelling was performed and, if so, what the decision was.

4. eCRF Baseline fetal echo 23+0 - 31+6

The baseline fetal echo is performed between 23+0 and 31+6 weeks. If an intervention is performed, the last exam before the intervention should be used as baseline fetal echo.

5. eCRF Additional baseline fetal echo 23+0 - 31+6

In case there is a late descision to perform an intervention, after a baseline fetal echo has already been submitted, there is an option to add an additional baseline fetal echo in the system.

6. eCRF Fetal interventions

A new eCRF Fetal interventions should be added for each intervention performed.

7. eCRF Follow-up fetal echo 33+0 - 34+6

The follow-up fetal echo is performed between 33+0 and 34+6 weeks.

8. eCRF Neonatal - Birth

Gestational age and size at birth, mode of delivery and pharmacological support.

9. eCRF Neonatal - Echo

First full study after birth, and before the first postnatal intervention, surgery or cath (except emergency atrial septostomy)

10. eCRF Neonatal - Cardiac clinical diagnosis

Cardiac diagnoses before the first intervention, surgery or cath (except emergency atrial septostomy)

11. eCRF Neonatal - Neonatal discharge

Type of circulation and clinical diagnoses at discharge.

12. eCRF Follow-up at 2 years of age

Type of circulation, clinical diagnoses, pulmonary hypertension, neurological sequealae, somatic growth.

13. eCRF Postnatal procedures

All cardiac surgical and catheter interventional procedures from birth to 2 years follow-up

14. eCRF Subject termination

Reason for subject termination including completion at 2 years of age.

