#### Inclusion of 100 intervention cases and 50 controls

The aim is to include at least 100 fetuses in the FAV 1+2 groups and 50 in the comparison group no-FAV 1+2. The largest numbers will likely be in FAV 1 and no-FAV 1 while the numbers in groups FAV 2 and probably also in no-FAV 2 will be smaller.

Assuming number of fetuses included as per above, 150 in total, and 30% success rate for the primary endpoint (=transplantation-free survival from fetal diagnosis to 2 years postnatal age, having a biventricular circulation without pulmonary hypertension at that time) in the no-FAV 1+2 group (9) and 60% success rate in the FAV 1+2 group, using alpha 0.05 and two-sided Fisher's exact test, a power of 91.8% would be able to be achieved. For a power of at least 80%, and all other assumptions unchanged, a success rate of 56% vs 30% in the FAV and no-FAV group, respectively, would be needed to be observed.

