2 STUDY POPULATIONS

2.1 Definition of Study Populations

2.1.1 Full Analysis Set for All Enrolled

Fetuses with severe MR and severe LA enlargement and/or intact or highly restrictive interatrial communication and/or cases with hydrops present at inclusion are all high-risk cases regarding survival, but may have a rather good prognosis if they survive the first critical period. It is likely they will be overrepresented in the FAV group to such a degree that it will be difficult to control for through propensity score matching. Therefore this subpopulation will be excluded from the full analysis set and analysed separately. Fetuses developing any of these conditions after inclusion will not be excluded from the full analysis set.

All enrolled fetuses that have satisfied inclusion/exclusion criteria and belong to FAV 1+2 and no-FAV 1+2 groups and not listed as belonging to the high-risk population described above will be included in the Full Analysis Set enrolled (FAS_{ENR}) population. Infants wrongly included in the study (not fulfilling all inclusion or fulfilling any of the exclusion criteria) will not be part of the FAS_{ENR} population, but will be described in the safety analyses. As detailed under 1.3.2, also subjects with exclusion criteria present at inclusion but diagnosed only after birth will be retrospectively excluded from the FAS_{ENR} population.

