2.1.6 Safety Population

All enrolled fetuses will be included in the safety population, also those wrongly included if such cases will exist.

Figure 5. Full analysis sets (FAS)

ToP=Termination of Pregnancy; IUD=Intrauterine Death; GW=Gestational Weeks; FAS=Full Analysis Set; FAV=Fetal Aortic Valvuloplasty

STATISTISKA KONSULTGRUPPEN	Statisti	cal Analysis Plan
Protocol: Effect of fetal aortic valvuloplasty on outcomes	Protocol No):
	Version: 1.0	Page 14 of 26

Figure 6. Per protocol populations (PP)

ToP=Termination of Pregnancy; IUD=Intrauterine Death; GW=Gestational Weeks; PP=Per Protocol; FAV=Fetal Aortic Valvuloplasty

Figure 7. Safety population

GW=Gestational Weeks; FAV=Fetal Aortic Valvuloplasty

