3.5 Safety Variables

3.5.1 Fetal Left Heart Growth

Change of dimensions of left heart structures and hemodynamics from the baseline fetal echo to the neonatal echo performed before the first postnatal intervention. The following variables will be analysed.

- Mitral valve diameter in diastole (z-score)
- Left ventricular inlet length (z-score)
- Direction of flow in the aortic arch (antegrade/retrograde)
- Left ventricular diastolic dimension (z-score)
- Left ventricular function
- Shunt direction through foramen ovale (left-to-right, right-to-left, bidirectional)

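### The exploratory left-heart growth models are listed on the Safety population, so high-risk case mix that the SAP sets apart re-enters the FAV versus no-FAV contrast; their time scale is also left open

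*SAP*

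**What the plan says.** - **Population.** SAP 7.1 titles Table 3.3.x "Mixed Models for Repeated Data Performed on ECHO Variables (Safety Population". SAP 2.1.6 defines that population: "All enrolled fetuses will be included in the safety population, also those wrongly included if such cases will exist". SAP 3.5.1, 4.1 and 4.7.1 set out the growth variables and method and name no population for the growth models.
- **High-risk fetuses.** SAP 2.1.1 and 2.1.5 single out fetuses that at inclusion have severe mitral regurgitation with severe left atrial enlargement, a closed or very restrictive atrial septum, or hydrops. SAP 2.1.1 expects them to be "overrepresented in the FAV group to such a degree that it will be difficult to control for through propensity score matching", and for that reason drops them from FAS_ENR and analyses them on their own.
- **Baseline echo.** The Protocol's eCRF section gives a window of 23+0 to 31+6 weeks for everyone, then adds: "If an intervention is performed, the last exam before the intervention should be used as baseline fetal echo". It gives no matching rule for no-FAV cases.
- **Time.** SAP 4.1 specifies mixed models for repeated data. It allows time to enter as visit or as continuous gestational age, with the choice to be made later.
- **Z-scores.** The Protocol's Z-scores section references fetal measurements to gestational age, but "Z-scores for postnatal cardiac measurements will be derived by body surface area". SAP 3.5.1 defines growth as "Change of dimensions of left heart structures and hemodynamics from the baseline fetal echo to the neonatal echo". The Protocol's Data analysis section also compares baseline with the follow-up fetal echo at 33+0 to 34+6 weeks.
- **Status.** SAP 4.1 and 4.7.1 call the growth analysis exploratory, and SAP 4.1 will still produce estimates, confidence intervals and p-values. Growth sits under the secondary objective and, if two papers are written, belongs to the first.

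**The concern.** The SAP gives a reason for keeping high-risk fetuses out of the efficacy comparison: it expects their share to differ between groups by more than matching can repair. That reason applies equally to a between-group comparison of left-heart growth, yet the only text naming a population for that comparison puts these fetuses back. If they grow differently from the rest, the groups will differ in mean growth with no treatment effect at all.

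The baseline rule raises a separate issue. In FAV the starting exam is set by the date of the procedure. In no-FAV it is any qualifying exam in a window almost nine weeks wide. If the analysis uses change between visits, the two groups may be followed over different lengths of gestation.

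At stake is how a published growth result can be read, in a study whose primary outcome arrives only two years after birth. No confirmatory conclusion depends on it.

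**Working it through.** **1. The plan's own figures.** The documents give no effect size, SD or power for growth. Their power figures concern the primary endpoint: "using alpha 0.05 and two-sided Fisher's exact test, a power of 91.8% would be able to be achieved", for 60% versus 30%. Exact enumeration of the two-sided Fisher test at 100 and 50 gives 92.7%, close to the stated value. This does not test the present point. Only the group sizes are carried forward: "The aim is to include at least 100 fetuses in the FAV 1+2 groups and 50 in the comparison group no-FAV 1+2".

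**2. Does adjustment cover the case mix?** The baseline echo confounders in SAP 3.1 are left ventricular diameter, inlet length, mitral diameter, aortic annulus, mitral inflow pattern and the LV:RV length ratio. Mitral regurgitation severity, left atrial enlargement, septal restriction and hydrops are not listed. SAP 4.1 names no covariates specific to the growth model. The listed confounders therefore do not directly carry the conditions that define high risk.

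**3. Case-mix artefact (all inputs assumed).** With no treatment effect, let h be the high-risk share in each group and D the difference in mean z-score change between high-risk and other fetuses, the same in both groups.

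Artefact = (h in FAV − h in no-FAV) × D

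| h FAV | h no-FAV | D | Artefact |
|---|---|---|---|
| 10% | 5% | 0.5 | 0.05 × 0.5 = 0.025 |
| 20% | 5% | 1.0 | 0.15 × 1.0 = 0.15 |
| 30% | 10% | 1.5 | 0.20 × 1.5 = 0.30 |
| 30% | 5% | 1.5 | 0.25 × 1.5 = 0.375 |

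For scale, with SD 1 (assumed), SE = √(1/100 + 1/50) = 0.173. The difference detectable with 80% power is (1.96 + 0.84) × 0.173 = 0.485 z. The artefact thus runs from 0.025/0.173 = 0.14 SE to 0.375/0.173 = 2.2 SE. Its sign follows the sign of D, which the documents do not give.

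**4. Baseline timing.** From the stated windows:
- Shortest interval from baseline to follow-up fetal echo: 31+6 to 33+0 = 8 days = 1.1 weeks.
- Longest interval: 23+0 to 34+6 = 83 days = 11.9 weeks.

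In an unadjusted visit-based model, the spurious difference = weekly z-score decline × difference between groups in mean baseline date. With an assumed decline of 0.05 to 0.15 z per week and a gap of 1 to 4 weeks, this is 0.05 × 1 = 0.05 to 0.15 × 4 = 0.60 z. The documents fix neither the gap nor its direction.

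**5. Two z-score references.** Suppose postnatal z = a + k × fetal z in both groups. The offset a cancels between groups, leaving (k − 1) × baseline imbalance. With k assumed at 0.8 to 1.2 and an imbalance of up to 0.5 z, that is at most 0.2 × 0.5 = 0.10 z, and zero when baselines are equal. Three of the six variables in SAP 3.5.1 are z-scores, and only the step to the neonatal echo changes reference.

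**The case against.** **The analysis is exploratory.** SAP 4.1 states that a small p-value here will not count as confirmation. This stands and limits the consequences. It does not remove bias from estimates that will be reported.

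**The population may be a listing slip.** It appears only in a table title. SAP 4.7.1 refers to General Methodology, where the main comparisons run on FAS_ENR, whereas SAP 4.7.2 to 4.7.4 name the Safety population explicitly. This may therefore be an inconsistency rather than a decision, and wrongly included cases may turn out not to exist. But no other text corrects the title, and a slip would still need correcting.

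**Timing is partly covered.** Gestational-age time is already permitted, SAP 4.1 says all analyses are adjusted, and gestational age at baseline echo is a potential confounder in SAP 3.1. This stands in part: the timing figures above apply only to a visit-based model without that adjustment. Listed confounders, however, enter only after a p<0.10 screen, and the time scale is left to be chosen later.

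**Stronger readings that the documents do not support.**
- A reader might infer that the plan wrongly presents the growth comparison as unbiased. Protocol Study design and SAP 1.2 claim freedom from bias only as regards differences between centres in postnatal treatment policy. Nothing here contradicts that.
- A reader might infer that changing z-score reference at birth biases the contrast by itself. Both groups use the same references, so a common offset cancels. Bias needs a group difference in baseline values, birth size or gestation at birth.
- A reader might infer that the inclusion echo could serve as baseline in both groups because the additional-baseline form holds the pre-procedure exam. That form is optional and covers only late decisions to intervene. An earlier baseline would also count untreated time as growth after FAV.

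**Conclusion.** The population point holds. As listed, the growth contrast includes fetuses whose expected imbalance the SAP itself regards as hard to control, and the listed confounders do not include their defining conditions. The contrast can therefore reflect case mix.

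The timing point holds conditionally: it matters if time is modelled by visit without adjustment, and the plan leaves that possible. The z-score references affect the interpretation of change up to the neonatal echo, and are a between-group bias only under the conditions given above.

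The size is not derivable from the documents. The case-mix range of about 0.03 to 0.38 z rests wholly on assumed shares and growth differences. Its low end is negligible; its high end is material against 0.485 z, the difference detectable at 100 and 50 with an assumed SD of 1. This is a correction worth making to an exploratory analysis. It does not touch the primary analysis.

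**What to change.** 1. Run the main growth models in Table 3.3.x on FAS_ENR. Show the high-risk population separately and keep the Safety population version as supportive. Name the population in SAP 4.7.1 so that text and table list agree.
2. Prespecify continuous gestational age as the time scale, with adjustment for gestational age at baseline echo.
3. Make the change from baseline to the 33+0 to 34+6 week fetal echo the main growth contrast. It uses one z-score reference and is already in the Protocol. Report the neonatal z-score, referenced to body surface area, separately.

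The work is SAP wording and table shells; no new data are needed. The real cost is sample size. If 20% to 30% of 100 FAV cases and 5% of 50 no-FAV cases were high-risk (assumed), 20 to 30 FAV and 2.5 no-FAV cases would leave the main model. With SD 1, the SE would rise from 0.173 to √(1/80 + 1/47.5) = 0.183 or √(1/70 + 1/47.5) = 0.188, an increase of about 6% to 9%. That loss is not trivial. It is larger when high-risk cases are common, which is also when pooling them is most likely to distort the contrast.

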7.2 Listing of Figures

Figure Number	Figure Title
1.x	For Baseline data
2.x	For Efficacy data
3.x	For Safety data
